#### 15.4 Enrolment Procedures- Retrospective arm

---

A retrospective patient is considered enroled in the clinical study if his records meet inclusion and exclusion criteria and has provided proper consent. Once subject is enroled, data will be extracted from the medical chart and entered into the study EDC.

#### 15.5 Patient Informed Consent – Retrospective arm

---

A consent form specific to the retrospective arm will be utilised to inform patient of the study, the chart review process and that Sponsor representatives and government bodies may access personal information. If consent is denied, or the patient is no longer reachable, the enrolment log will record reason, and no further data will be collected or retained. At least three attempts, using multiple methods, should be used to contact potentially eligible patients, at the discretion of the PI.

#### 15.6 Subject Withdrawal Procedure – Retrospective arm

---

Any subject who has provided consent may elect to withdraw their consent. The reason for withdrawal will be recorded, and their data will be excluded.

#### 15.7 Mitigating potential sources of error

---

There are many sources of bias in retrospective series; therefore, a checklist of potential biases along with proposed solutions was created to aid in the design of this study (**Table 12**). The checklist is based on the work of Kaji et al, Gilbert et al and Walker and Nowacki.

---

 Walker E., Nowacki,AS. Understanding Equivalence and Noninferiority Testing J Gen Intern Med. 2010 26(2):192-6.

**Table 12 Retrospective Chart Review Design Quality Checklist**

Issue and Suggested Solution		Study Design
Chart Review Inappropriate for Study Question		

 
Establish whether necessary information is available in the chart.
 
Define outcome variables to be collected a priori.
 
Establish if there are sufficient charts to perform the analysis with adequate precision.
 
		
 
Participating sites are research centres, two sites have presented their own UroLift datasets at medical conferences.
 
The EDC system (host of the eCRFs) and source worksheets will guide the abstractor on exact data collection requirements.
 
Participating PIs were qualified due to their high number of BPH patients they treat.
 

Investigator Conflict of Interest or Bias		

 
Declare any conflict of interest.
 
Provide evidence of Ethics Committee approval.
 
Submit the data collection form, as well as the coding rules and definitions.
 
		
 
Financial Disclosure and conflict of interest forms will be completed by all Principal Investigators.
 
A regulatory binder will be maintained for HRA and EC correspondence including approval materials.
 
Study will utilise EDC with eCRF completion instructions. MedDRA coding will be used and embedded in the EDC.
 

Patient Sample is Non-Representative		

 
Case selection or exclusion using explicit protocols and well described the criteria.
 
Ensure all available charts have an equal chance of selection.
 
		
 
Study design requires that all surgeries during a set amount of time are evaluated for inclusion, and criteria are well matched to the prospective investigation.
 
The NHS trust system is consistent across centres.
 

Chart Abstraction is Not Systematic (Misclassification Bias)		

 
Use standardised abstraction forms to guide data collection
 
Provide precise definitions of variables
 
Pilot test the abstraction form
 
		
 
EDC will be used with training, written guidelines.
 
The EDC has been used extensively by Sponsor and can be modified with minimal time and sacrifice to study.
 

Presence of Missing or Conflicting Data		

 
Ensure uniform handling of data that is conflicting, ambiguous, missing, or unknown
 
Perform a sensitivity analysis if needed
 
		
 
Handling of missing data for endpoint evaluation is described a priori in clinical protocol
 

Abstractors Biased or Not Blinded		

 
Blind chart reviewers to the etiologic relation being studied or the hypotheses being tested.
 
		
 
All data will be abstracted. Blinding is not applicable.
 

Abstractors Not Sufficiently Trained		

 
Train chart abstractors.
 
Describe the qualifications and training of the chart abstractors.
 
		
 
Abstractor training process will include collaborative review of mock medical chart and EDC entry to test environment.
 

Issue and Suggested Solution	Study Design

 
• Ideally, train abstractors before the study starts, using a set of “practice” medical records.
 
• Ensure uniform training, especially in multi-centre studies
 
	
 
• CV of individual(s) will be evaluated.
 

Abstractors not sufficiently monitored	

 
• Monitor the performance of the chart abstractors
 
• Hold periodic meetings with chart abstractors and study coordinators to resolve disputes and review coding rules.
 
	
 
• NeoTract will monitor and audit on a periodic basis 100% source verification
 
• A written monitoring plan will be established prior to study commencement and revision controlled throughout the study.
 
• Newsletters will be issued and RC meetings will be held
 

Chart Abstraction Unreliable	

 
• A second reviewer should re-abstract a sample of charts, blinded to the information obtained by the first correlation reviewer.
 
• Report a kappa-statistic, intra-class coefficient, or other measure of agreement to assess inter-rater reliability of the data
 
• Provide justification for the criteria for each variable
 
	
 
• Sites will be audited according to an a priori audit plan prior to finalisation of data sets
 
• Analysis of inter-rater reliability of the data may be conducted
 
• Study variables are derived from clinical investigations and used for consistency between the study arms.
 

Sources of Error from the Use of Electronic Medical Records	

 
• The use of boilerplates, items copied and pasted, default tick boxes and delays in time stamps relative to actual care.
 
	
 
• Manual data entry will be required and EDC designed to prohibit serial data entry.
 
• A customised source documentation plan for each site utilising their medical record systems will be developed.
 

## 15.8 Case Abstraction: Data Collection

### 15.8.1 Screening

The following medical history parameters will be collected from time when patient presented with AR.

 
• Inclusion/Exclusion confirmation
 
	
 
• Prostate volume (cc) by ultrasound or other methods
 
	
 
• History of BPH: length of time, symptom scores, treatments sought
 
	
 
• Catheterisation and TWOC history
 

 
• Co-morbidities
 
	
 
• Uroflowmetry/PVR within 6 months prior to intervention
 
	
 
• IPSS within 6 months prior to intervention
 
	
 
• Other GU treatments
 

### 15.8.2 Procedure

The following will be collected (if available):

• Date, duration	• Type of facility, type of surgery	• Complications, adverse events (urological, sexual function, cancer and SAEs)	• Duration of hospital stay
• Catheterisation	• Pathology (documentation only)		

### 15.8.3 Post-procedure

The following post-surgery data will be collected for period after discharge through 12 months after their surgical intervention (if available):

• Date of contacts	• Type, reason of contact (phone, office visit)	• Complications, adverse events (urological, sexual function, cancer and SAEs)	• Interventions
• BPH medications, indication	• Symptom scores	• Uroflowmetry/PVR	• Catheterisations

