## 7 Study Design

---

The study is a multi-centre, consecutive, prospective feasibility study of the UroLift System in acute urinary retention (AR) patients. A retrospective dataset (patients treated from June 1, 2015 to December 31, 2015) of patients meeting similar criteria that underwent an invasive procedure to treat AR will be analysed against UroLift data. A maximum of 55 subjects undergoing UroLift will be enroled in up to six study centres in Great Britain. This feasibility study is the first to assess patients undergoing PUL with AR and will determine if a larger, quantitative study should be conducted with optimal methodology. By evaluating results pertaining to study design, primary study assessment, conduct of trial, site performance, subject compliance, and inclusion criteria specifically, a robust safety and effectiveness study can follow.

Clinical improvements will be assessed at post-procedure, 6 weeks, and months 3, 6, and 12 post-index procedure.

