## 14.5 Adverse Event Reporting

Adverse events will be collected on all enroled subjects. Subjects will be asked about adverse events at each visit, and all AEs will be documented and reported regardless of relatedness.

Adverse events will be documented on the AE electronic case report form (eCRF) within the study's Electronic Data Capture System (EDC).

When an SAE occurs, the Sponsor should be notified within 24 hours of site awareness via completion of the AE eCRF in the EDC System. Sponsor will receive an alert upon any SAE entry and will be responsible for reporting to notified body, ethics committee and all other participating investigators as applicable. Should Sponsor determine, either through investigator reports or in-house testing, that a unexpected SAE presents an unreasonable risk to all participating subjects, Sponsor will suspend the clinical investigation.

It is the responsibility of the Chief Principal Investigator to report all related and unexpected Serious Adverse Events (SAEs) to the ethics committee. The Sponsor may report on behalf of the Chief Investigator. Device-related SAEs in this study, using a CE-marked device in a post-market surveillance study, are reportable to the MHRA Adverse Incident Centre as reported under the requirements of the Devices Vigilance requirement.

Annual and final reports will be provided to the EC as applicable per EC requirements with Sponsor assistance.

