### 16.4 Missing Data

---

To protect the scientific integrity and validity of study, a robust data retention plan will be employed through 12 months and reasons for missing data or early exit will be collected. No imputation for missing data points is planned.

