### **Retrospective Arm**

The following baseline and procedural data points will be summarised for both the retrospective and the prospective arms. Although the study is not powered to make comparisons between the retrospective surgical patients and the prospective Urolift subjects, comparisons in the observed data will be made statistically. Continuous variables will be compared using a t-test or non-parametric alternative, binary data points will be compared using chi-square or Fisher's exact test.

- 1) Baseline demographics

- 2) Duration of catheterisation to procedure (days)
- 3) Procedure time
- 4) Hospitalisation time

The following outcomes post procedure will be summarised for the retrospective surgical group and will compared to the results obtained in the prospective study. The statistical significance of any observed differences will be assessed.

- 1) Total numbers of related AE, SAE, and Clavien-Dindo  $\geq$ IIb individually
- 2) Percent procedure/device related AE rates by month post index procedure and by severity
- 3) Retreatment post index intervention by time to event and by month
- 4) Medical treatment post index intervention by time to event and by month
- 5) Urinary retention recurrence rates at 1 month, 6 weeks and at 3, 6 and 12 months
- 6) Post-procedure TWOC success percent
- 7) Catheterisation use

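### Section 16.6 tests chart-recorded surgical events against visit-solicited PUL events with no like-for-like event set, denominator or censoring rule for the surgical arm, so surgical event rates are likely understated

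*Combined protocol and SAP*

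**What the plan says.** **Surgical arm.** Events come from chart abstraction. For the procedure, Section 15.8.2 says: "The following will be collected (if available". After discharge, Section 15.8.3 says: "The following post-surgery data will be collected for period after discharge through 12 months after their surgical intervention (if available". In both sections the AE field is limited to "Complications, adverse events (urological, sexual function, cancer and SAEs". Section 15.8.3 also abstracts the date, type and reason of each contact.

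**PUL arm.** Section 14.5 says: "Subjects will be asked about adverse events at each visit, and all AEs will be documented and reported regardless of relatedness". Section 7 sets the schedule: "Clinical improvements will be assessed at post-procedure, 6 weeks, and months 3, 6, and 12 post-index procedure". Table 7 repeats catheterisation, intervention and AE review at all five of these visits.

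**Comparison.** Section 16.6 (Retrospective Arm) compares, among other outcomes, total related AEs, related AE percentages by month and severity, retreatment and medical treatment (both by time to event and by month), and "Urinary retention recurrence rates at 1 month, 6 weeks and at 3, 6 and 12 months". Statistical significance is to be assessed, although the same section says that the study is not powered for the comparison.

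**Missing data.** In Section 15.7, Table 12 lists missing chart data as a source of error and answers: "Handling of missing data for endpoint evaluation is described a priori in clinical protocol". Section 16.4 supplies a retention plan, collection of the reasons for missing data, and "No imputation for missing data points is planned".

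**The concern.** The two arms differ in how an event comes to be counted, as well as in treatment. A mild symptom that a PUL man reports because he is asked is counted. The same symptom in a surgical man is counted only if he sought care, someone wrote it down, and it falls in one of four categories. A significance test on the resulting rates partly tests this difference in ascertainment.

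Comparing PUL with surgery is a stated objective (Section 6.1), Section 13.9 looks to it to show the benefit of PUL, and the results are to inform a larger trial (Sections 7 and 16.7). If surgical events are under-recorded, PUL looks relatively worse than it is, and the surgical event rates carried into the planning of the next trial are too low.

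**Working it through.** The plan has no figure to reproduce: 55 is a cap on PUL enrolment, no surgical sample size is given, and no alpha or power is stated for the comparison.

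**Step 1: does any rule cover a surgical man with a silent chart?**

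- Section 16.4 rules out imputation. It does not say whether a man without recorded contact counts as event-free or leaves the denominator.
- The Kaplan-Meier paragraph of Section 16.6 starts the clock at the PUL procedure. It uses the ITT and per-protocol populations, and the safety population for retention. ITT and safety require a UroLift device to have been introduced, and per-protocol is a subset of ITT. None can contain a surgical man.
- The 100% source verification in Table 12 checks entries against the chart. It cannot show what the chart never recorded.
- Retreatment and medical treatment are listed by time to event for the surgical arm, but without a censoring rule. AE percentages and retention recurrence have no time-to-event method for that arm.

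**Step 2: what would unequal capture do?** This is an illustration.

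Inputs: 55 PUL men (the cap in Section 7). Assumed: 55 surgical men (30 and 100 also run), a true rate of 20% in both arms (50% also run), capture fraction *c* from 40% to 100%, and two-sided Fisher's exact test at 0.05. Section 16.6 names that test for binary baseline and procedural items but names none for the outcomes.

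Observed surgical rate = true rate × *c*. The probability that PUL appears significantly worse is the sum of Bin(a; 55, p) × Bin(b; n, p·c) over all tables with Fisher p ≤ 0.05 and a/55 > b/n.

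| Capture *c* | Observed surgical rate (true 20%) | P(PUL significantly worse), 55 v 55, true 20% | Same, true 50% |
|---|---|---|---|
| 100% | 20% | 0.014 | 0.014 |
| 80% | 0.20 × 0.80 = 16% | 0.046 | 0.127 |
| 60% | 0.20 × 0.60 = 12% | 0.136 | 0.491 |
| 40% | 0.20 × 0.40 = 8% | 0.335 | 0.891 |

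At 60% capture and a true 20%, the probability is 0.114 with 30 surgical men and 0.229 with 100. If surgery is truly worse (50% against 25%, 55 v 55), the power to show it falls from 0.72 at full capture to 0.32 at 80% and 0.06 at 60%.

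**Step 3: does the denominator matter?** Keep the true rate at 20%. Let *r* be the share of events recorded and *f* the share of event-free men with a contact.

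- All enrolled charts: 0.20 × r.
- Charts with a contact: 0.20r / (0.20r + 0.80f).

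| *r* | *f* | All charts | Charts with a contact |
|---|---|---|---|
| 60% | 50% | 12% | 0.12/0.52 = 23.1% |
| 60% | 70% | 12% | 0.12/0.68 = 17.6% |
| 60% | 90% | 12% | 0.12/0.84 = 14.3% |
| 90% | 50% | 18% | 0.18/0.58 = 31.0% |

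The choice of denominator can remove or reverse the bias. The two figures need not bracket the truth: in the third row both lie below 20%. Neither is safe as the sole analysis.

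**The case against.** The strongest reply has four parts.

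1. **The plan does not say that silence means no event.** A reader might infer that a man with no note after week 6 stays in the 12-month denominator as event-free. No section says so, and the ban on imputation arguably points the other way. This stands. The defect is that the denominator is undefined.
2. **Part of the remedy is already planned.** Retreatment and medication are listed by time to event, and such an analysis needs an end-of-observation date, so it cannot be said that the contact dates will go unused. This stands for those two outcomes, except that the surgical censoring rule is missing. It does not reach AE percentages or retention recurrence.
3. **The direction is not all one way.** Section 16.6 compares related AEs, which narrows the gap. Several rules lower PUL counts: recurrent retention is not an AE (Section 14.3), only urological SAEs are reported between an alternative surgery and the 12-month visit (Section 10.10.1), and AE analysis is censored at that surgery (Section 16.3). The documents do not say whether these rules apply to the surgical arm. SAEs and re-operations are also more likely to reach a chart than mild events. This limits the claim to a likely understatement that falls mainly on low-grade events.
4. **The comparison is exploratory.** It is declared unpowered and Section 16.7 sets no success criteria. That bears on precision and on decisions. It does not remove a systematic difference in how events are found.

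**Conclusion.** The point holds in a limited form. As written, Section 16.6 tests outcomes that are ascertained differently in the two arms, and no denominator or censoring rule applies to the surgical arm. Surgical event rates are likely understated relative to PUL, mainly for low-grade events. This rests on the judgement that charts miss mild events more often than direct questioning does.

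The size cannot be derived. A reader might multiply an assumed 20% rate by 60 to 80% coverage and conclude that surgical rates are 4 to 8 points too low (0.20 × 0.20 to 0.20 × 0.40). The documents do not support that as a finding: the coverage is not given, coverage of follow-up time is not the same as capture of events because retention and re-operation themselves generate contacts, and the sum assumes that every chart stays in the denominator. The probabilities in the first table show how sensitive the test is to unequal capture. They do not estimate what will happen in this study.

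**What to change.** Add to Section 16.6 (Retrospective Arm):

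1. **Like-for-like AEs.** For the between-arm comparison, apply the retrospective categories (urological, sexual function, cancer, SAEs) to both arms. Limit significance tests to events that led to medical care, such as SAEs and interventions. Present all other between-arm AE comparisons as descriptive.
2. **Time-to-event outcomes.** Estimate retention, retreatment and medication in the surgical arm by Kaplan-Meier, censored at the last documented contact, to match the method already set for PUL.
3. **AE percentages.** Report them over all enrolled charts and over charts with adequate contact, defined in advance, as a lower and an upper figure for the choice of denominator. Give contact completeness by time point beside them. Do not use men with a contact at or after the time point as the sole denominator: it favours men who came back with problems and drops a man with an early event and no later note.

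The cost is SAP wording. Contact dates and AE categories are already abstracted under Section 15.8.3. Surgical-arm intervals will be wider. Censoring at last contact may be informative, because men with problems return more often, and the report should say so.

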## 16 Study Data Analysis

---

All effectiveness analyses will be performed on the “intent-to-treat (ITT)” group. All subjects who were enroled with at least one UroLift device introduced will be included in the intention to treat analysis. Effectiveness assessments for enroled subjects whom later undergo surgical retreatment with either PUL or with any other surgical procedure will be censored the day after the secondary intervention. Censoring in adverse event analysis will be applied only to alternative surgical retreatments and not to secondary PUL.

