## 1 Protocol Summary

Study Title	Prostatic Urethral Lift in Subjects with Acute Urinary Retention Study (PULSAR)
Study Objectives	Assess feasibility and safety of the Prostatic Urethra Lift (PUL) procedure in patients with acute urinary retention secondary to BPH. Research methodology will also be evaluated for larger, randomised study.
Study Design	Multi-centre, prospective evaluation of PUL and retrospective review of invasive surgery as potential comparator.
Sample Size	Up to 55 subjects treated with PUL. Retrospective chart review will include BPH patients that presented with AR and went on to de novo invasive surgery from June 1, 2015 to December 31, 2015.
Subject Population	Males over the age of 50 diagnosed with symptomatic benign prostatic hyperplasia (BPH) and ongoing acute urinary retention after failed TWOC.
Number of Centres (Sites)	Up to six centres in the United Kingdom.
Clinical Indication	The UroLift System is indicated for the treatment of symptoms due to urinary outflow obstruction secondary to benign prostatic hyperplasia (BPH) in men 50 years of age or older.
Primary Study Assessment	Successful post-procedure voiding trial without catheter (2-4 days).
Safety Assessment	Rate of serious adverse events (SAEs) related to BPH intervention through 3 months.
Additional Assessments	1. Need for further clean intermittent self-catheterisation (CISC) 2. Urinary symptoms, post void residual (PVR) and peak flow rate over follow-up 3. Subjects free from urinary retention through 1 month, 6 weeks, 3, 6 and 12 months 4. Subjects free from alternative surgical procedure for BPH through 12 months 5. Duration of catheter prior to treatment and in follow-up between prospective (PUL) and retrospective (TURP/HoLEP) 6. Rate of AEs in prospective PUL and retrospective TURP/HoLEP 7. Assess enrolment rate, willingness of patients to enrol, inclusion criteria, and appropriateness of endpoint
Follow-up Evaluations	Post-procedure, 6 weeks, 3 months, 6 months (remote), 12 months
Anticipated Study Duration	
First patient in (FPI)	15-April-2018
Last patient in (LPI)	31-December-2018
Endpoint analysis	28-February-2019
Study close	01-April-2020

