**Table 2 Definitions**

Adverse event (AE)	An adverse event (AE) is defined as any undesirable medical occurrence in a clinical trial subject, whether it is considered to be related to the device or not, that includes a clinical sign, symptom, or condition.  Once a subject is enroled, all AEs must be reported through follow-up period. Only exacerbated conditions or new onset qualify as an AE. Principal Investigator will assess severity, relatedness, serious or unexpected.
Alternative Surgical Intervention	A post-index procedure surgery, other than PUL, to treat BPH.
Acute Urinary Retention	Painful inability to void and a residual volume < 1500 mL.
Invasive BPH surgery	
 
• Transurethral resection of the prostate (TURP)
 
• Transurethral Laser (PVP, HoLEP or Interstitial)
 
• Open Prostatectomy
 

Index procedure	The first procedure to which subjects are enroled.
Precipitated AR	Acute urinary retention that develops in response to a trigger such as UTI, anaesthesia, surgery, medications with sympathomimetic or anticholinergic effects.
Serious Adverse Event (SAE)	
Serious Adverse Event (SAE) is defined as untoward occurrence that: (a) results in death; (b) is life-threatening; (c) requires hospitalisation or prolongation of existing hospitalisation (d) results in persistent or significant disability or incapacity; (e) consists of a congenital anomaly or birth defect; or (f) is otherwise considered medically significant by the investigator.
 
(in-patient hospitalisation is at least 24 consecutive hours)

Unexpected Adverse Event	An unexpected adverse event is an event which by nature, incidence, severity or outcome has not been identified in the current version of the Sponsor risk management files.
Spontaneous AR	Associated with older age, BPH, elevated PSA, or presence of severe LUTS.
PUL Procedure Time	Time from first device insertion to last device removed.

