## 6.4 Other Assessments

---

Several other outcomes will be analyzed during the 12 month follow-up to understand post-TWOC durability:

- Catheter free rate and days free from catheter at 1 month and throughout follow-up
- Number of subjects who failed initial attempt but are able to void in subsequent TWOC
- Need for further clean intermittent self-catheterisation (CISC)
- Urinary symptoms peak flow rate, post void residual (PVR) volume
- Subjects free from alternative surgical procedure for BPH
- Duration of pre-index procedure catheter and its impact on durability
- Rate of adverse events
- The prospective arm will be compared to the available data collected in the retrospective surgical arm

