#### 10.10.2 Secondary PUL

A subject undergoing a procedure for UroLift implant removal (misplaced) or additional implant(s) placement will remain on their original follow-up visit schedule.

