### 16.3 Safety Population

---

The safety population will be used for all safety assessments. The safety population includes all enroled subjects with at least one UroLift device introduced. Safety assessments for enroled subjects whom later undergo surgical retreatment with any other surgical procedure will be censored on the day of the secondary intervention. Censoring in adverse event analysis will be applied only to alternative surgical retreatments and not to secondary PUL.

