## 16.6 Additional Assessments

---

Continuous measures will be summarised by visit. Summary statistics will include the available sample size, mean and standard deviation. Changes from baseline to each follow-up visit will also be calculated and the summary statistics will include the number of patients with change score available, mean, median, standard deviation, and confidence intervals (CI). These assessments will be calculated for both the ITT and PP analysis populations.

The Kaplan-Meier method will be used to calculate freedom from alternative secondary surgery over time and freedom from medical treatment, from the time of the PUL procedure for the ITT and PP populations. Subjects that do not have an alternative procedure will be censored at their last recorded follow-up visit. The probability of freedom from urinary retention will be analysed in a similar manner for the safety population. Time without catheter will be analysed using the Kaplan-Meier method in the ITT and PP populations.

Adverse events will be summarised by overall adverse events (AEs), severe AEs (grade 3 or higher on CTCAE scale), AEs related to device and/or procedure, serious adverse events (SAEs) and SAEs related to device and/or procedure. Adverse events will be coded using MedDRA and CTCAE v4.0 severity grades and will be presented by System Organ Class (SOC) and preferred term. Adverse events will be summarised for the safety population.

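### Section 16 censors effectiveness at repeat PUL but the Kaplan-Meier text in 16.6 does not, and nothing says which rule governs freedom from alternative surgery

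*Combined protocol and SAP*

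**What the plan says.** The opening of Section 16 assigns effectiveness analyses to the ITT group. It then states that effectiveness assessments for enrolled men who go on to "surgical retreatment with either PUL or with any other surgical procedure will be censored the day after the secondary intervention". Repeat PUL is named as a censoring event.

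Section 16.6 specifies the curve itself: "The Kaplan-Meier method will be used to calculate freedom from alternative secondary surgery over time and freedom from medical treatment", from the PUL procedure, in the ITT and PP populations. Its censoring rule is "Subjects that do not have an alternative procedure will be censored at their last recorded follow-up visit". Repeat PUL does not appear. Time without catheter is also a Kaplan-Meier analysis in ITT and PP, and 16.6 gives it no separate rule for repeat PUL.

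Three other places matter:

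- Table 2 defines alternative surgical intervention as "A post-index procedure surgery, other than PUL, to treat BPH", so a repeat PUL is not an event on this curve.
- Section 10.10.2 says that men with a secondary PUL "will remain on their original follow-up visit schedule", so later surgery would be recorded.
- Section 16.3 exempts secondary PUL, but for safety: "Censoring in adverse event analysis will be applied only to alternative surgical retreatments and not to secondary PUL". No such exemption is written for effectiveness.

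**The concern.** The two rules give different data for the same man. Take a repeat PUL at month 4 and a TURP at month 9. Under 16.6 he has an event at month 9. Under Section 16 he is censored event-free just after month 4, and a surgery that the study observed does not enter the estimate. A direct alternative surgery is not affected, because censoring takes effect the day after it.

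A Kaplan-Meier estimate treats censored men as having the same later risk as those who remain. Men who have needed a second procedure may well have a higher risk, so censoring them there is plausibly informative.

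Freedom from alternative surgery through 12 months is an additional assessment in the Protocol Summary. Section 6.4 also lists it, under the aim "Several other outcomes will be analyzed during the 12 month follow-up to understand post-TWOC durability". Section 16.6 further compares time to retreatment with the retrospective surgical arm and assesses significance. Section 16 states its repeat-PUL rule for UroLift subjects and the plan states no counterpart for the surgical arm, so an unsettled rule could also affect that comparison.

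**Working it through.** The plan gives no event rate, repeat-PUL rate or target for this curve, so it has no figure to reproduce. The check compares the two rules on the same invented data.

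**From the documents.** N = 55, the maximum (Protocol Summary: "Up to 55 subjects treated with PUL"). Follow-up is 12 months.

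**Assumed.** *a* men have direct alternative surgery at day 180. *k* men have repeat PUL at day 120, of whom *j* have alternative surgery at day 240. Everyone else is followed to day 365.

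**Formulas.**

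- 16.6 rule: nobody is censored before day 365, so S = (N − a − j)/N.
- Section 16 rule: *k* men leave at day 121, before any event, and the *a* events fall among the N − k still at risk, so S = (N − k − a)/(N − k).

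| a / k / j | 16.6 rule | Section 16 rule | Difference (points) | Per lost event |
|---|---|---|---|---|
| 5 / 1 / 1 | 49/55 = 89.1% | 49/54 = 90.7% | 1.6 | 1.6 |
| 5 / 3 / 1 | 49/55 = 89.1% | 47/52 = 90.4% | 1.3 | 1.3 |
| 5 / 3 / 3 | 47/55 = 85.5% | 47/52 = 90.4% | 4.9 | 1.6 |
| 5 / 5 / 3 | 47/55 = 85.5% | 45/50 = 90.0% | 4.5 | 1.5 |
| 5 / 5 / 5 | 45/55 = 81.8% | 45/50 = 90.0% | 8.2 | 1.6 |
| 8 / 5 / 3 | 44/55 = 80.0% | 42/50 = 84.0% | 4.0 | 1.3 |
| 0 / 3 / 3 | 52/55 = 94.5% | 52/52 = 100% | 5.5 | 1.8 |
| 0 / 5 / 5 | 50/55 = 90.9% | 50/50 = 100% | 9.1 | 1.8 |
| 10 / 5 / 5 | 40/55 = 72.7% | 40/50 = 80.0% | 7.3 | 1.5 |

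**Timing.** For 5/3/3, moving repeat PUL between days 60 and 200 and the later surgery between days 90 and 330 leaves the 16.6 figure at 85.5%. The Section 16 figure moves only between 90.4% and 90.9%.

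**Direction.** With the timings in the table, the difference is (a + j)/N − a/(N − k). It is positive exactly when j/k > a/(N − k), that is, when repeat-PUL men go on to surgery more often than the others have it directly. Every row meets this condition. If no repeat-PUL man has later surgery, no event is lost and only the risk set shrinks: 5/3/0 gives 50/55 = 90.9% against 47/52 = 90.4%, which is 0.5 points lower under Section 16.

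**The case against.** The strongest reply is that 16.6 is the specific text for this curve and should override a general opening paragraph. Section 16 speaks of effectiveness assessments, which can be read as visit measures such as IPSS, Qmax and PVR. On that reading the later TURP is counted and nothing is lost. This is a fair reading, but the documents do not establish it. The curve is run in the populations used for effectiveness, and the only exemptions for secondary PUL concern safety. An analyst could follow Section 16 to the letter.

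The second reply is that little depends on the result. The event counts are invented, and for 47/55 the standard error is √(0.855 × 0.145/55), about 4.8 points, so the 4.9-point gap is about one standard error. Section 16.7 sets no success criterion. Section 10.11 has an independent urologist judge treatment failure for each man, with prescribed surgery among the items reviewed. All of this stands and limits the point to a clarification. It does not settle which rule applies, and a shift caused by the censoring rule is not sampling error.

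A reader might infer more than the documents support:

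- **Every repeat PUL marks a failed first procedure.** Section 10.10.2 also covers removal of misplaced implants, so informative censoring is likely but not established.
- **The retention curve is affected too.** It uses the safety population, and under 16.3 only other surgery censors there.
- **No analysis of any retreatment is planned.** Item 3 of the post-procedure outcomes under Retrospective Arm in 16.6 already lists retreatment by time to event. It does not say whether secondary PUL counts.
- **This is the main durability result.** Section 6.4 lists it as one of several outcomes.

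**Conclusion.** The point holds as an unresolved conflict between two censoring rules, affecting the ITT/PP alternative-surgery curve and, through the same Section 16 rule, the time-without-catheter curve. It is not a demonstrated bias: if 16.6 governs, no event is lost.

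If Section 16 governs, any alternative surgery after a repeat PUL drops out. Twelve-month freedom is then overstated whenever these men go on to surgery more often than the rest. In the scenarios with at least one lost event, the overstatement is 1.3 to 9.1 points in total, or about 1.3 to 1.8 points per lost event at N = 55. The stronger statement that the estimate must be biased upward is not supported. It requires both the Section 16 reading and surgery that actually follows repeat PUL. The size rests wholly on assumed counts. Importance is minor, because the study is descriptive and has no success threshold.

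**What to change.** 1. In 16.6, state that secondary PUL is not a censoring event for the alternative-surgery and time-without-catheter curves, and that men are followed to the event or to their last visit.
2. In Section 16, confine censoring at repeat PUL to visit-based measures such as IPSS, Qmax and PVR.
3. In item 3 of the post-procedure outcomes under Retrospective Arm in 16.6, state that secondary PUL counts as an event in the time-to-retreatment analysis, and report that result beside freedom from alternative surgery.

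Leave the retention curve as it is. The cost is a few sentences. Men with a secondary PUL keep their visit schedule, and Table 7 includes an intervention review at every follow-up visit, so no new data are needed.
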